APPENDIX 1: MODIFIED AUTO-INFLAMMATORY DISEASE ACTIVITY INDEX

Fever > 100.4	Abdominal Pain/Colic	Nausea/vomiting	Diarrhea	Transaminitis	Organomegaly	Rash	Uveitis 3+/4+	Uveitis 1+/2+	Arthralgia	Arthritis	Radiologic CNS involvement	CNS symptoms	Cytopenia (HgB < 9.0, PLT < 100, WBC < 3.0)
0/1	0/1	0/1	0/1	0/1	0/1	0/1	0/2	0/1	0/1	0/1	0/1	0/1	0/1

mAIDAI component	Identified subjective component	Included in objective evaluation of response to therapy and disease reactivation
Fever >100.4 F/38C		X
Abdominal Pain/ Colic	X	-
Nausea/Vomiting	X	-
Diarrhea		X
Transaminitis		X
Organomegaly		X (separated into hepatic and lymphatic system)
Rash		X
Uveitis 3+/4+		X
Uveitis 1+/2+		(all grades grouped together to create an unweighted scale)
Arthralgia	X	-
Arthritis		X
Radiologic CNS involvement		X
CNS symptoms	X	-
Cytopenia (HgB <9.0, PLT <100, WBC <3.0)		X

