10.5 Blinding/unblinding Arrangements

Sponsor, patients, investigators, investigator staff, persons performing the assessments, and data analysts will remain blinded to the identity of the assigned study treatment from the time of randomization into the RW phase until the final database lock, using the following methods:

- 1) Randomization data are kept strictly confidential until the time of unblinding, and will not be accessible by anyone else involved in the treatment administration, treatment outcome assessment or data collection or analysis, with the exception of the DSMB members as described in the DSMB Charter.
- 2) The identity of the treatments will be concealed by the use of study drugs (Tadekinig alfa and Placebo) that are all identical in packaging, labeling, schedule of administration, appearance and odor.
- 3) The randomization code for an individual patient may only be unblinded in emergency situations, where the investigator decides that a patient cannot be adequately treated without knowing the identity of their treatment allocation. To break the randomization code, the investigator must open the emergency unblinding envelopes provided. If any unblinding envelope is opened, the time, date, subject number and reason for opening must be documented.

The primary endpoint, time to first disease reactivation, is a parameter which is objectively assessed by reporting a time and measuring serum ferritin levels, serum CRP and assessing mAIDAI. mAIDAI is comprised of 14 items of which 4 symptoms could be considered subjective and thus are excluded from the definition of response to therapy and disease reactivation (see Appendix I). All 14 items will continue to be collected and will be plotted over time in the descriptive analysis.

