As sensitivity analyses, change from baseline to maximum post-baseline score and change from baseline to last RW assessment up to the start day of rescue immunosuppression treatment will be summarized and compared among treatment groups. In addition, the mean change from RW baseline in the mAIDAI total score will also be compared among treatment groups using Welch's two-sample t-test that allows for unequal variances, as well as by a linear regression model with Huber-white sandwich errors allowing for heteroscedasticity. A rank ANCOVA model to include a covariate for the RW Baseline score will also be performed as sensitivity analysis, similar to the analysis of CRP and serum ferritin changes from RW Baseline. Model estimates for the linear regression model and the rank ANCOVA model will be presented to include the estimate of mean treatment difference, associated standard error, 95% CI of the mean difference, and p-value.

Shifts in mAIDAI responses from RW Baseline to each post-baseline visit during the RW phase will be summarized by component and treatment group (ie, present or absent at

baseline to present or absent at each post-baseline visit). Summarization will include the total counts for all responses reported at both RW Baseline and each post-baseline visit. Percentages will be based on the number of patients with a non-missing RW Baseline and non-missing post-baseline assessment at each visit.

The number and percent of patients who improve within each component (objective and subjective) of the mAIDAI will be summarized during the RW phase by visit and treatment group. For each component, only the number of patients who reported the assessment as present (1 or 2) will be considered for analysis. The proportion of patients who report the assessment as absent (0, ie, improved relative to baseline) at each post-baseline visit during the RW phase will be compared among treatment groups using the Fisher's exact test. Patients with a missing assessment at a post-baseline visit will be considered to have not improved.

Descriptive statistics for the mAIDAI total score and changes from baseline during the SAOL phase will be presented by visit. Shifts in mAIDAI responses from baseline during the SAOL phase will be presented by visit. The number and percent of patients who improve within each component of the mAIDAI during the SAOL phase will be presented by visit.

7.4.4.5 *Physician's Global Assessment*

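### In the SAP 7.4.4.4 component tables, uveitis that worsens from 1+/2+ to 3+/4+ counts as improved if one grade is recorded per visit

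*Protocol*

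**What the plan says.** Protocol Appendix 1 lists two uveitis columns among the mAIDAI components: 3+/4+, scored 0 or 2, and 1+/2+, scored 0 or 1. Protocol 10.5 gives the item count: "mAIDAI is comprised of 14 items of which 4 symptoms could be considered subjective". In the second table of Appendix 1 the two grades are merged ("all grades grouped together to create an unweighted scale"), but that note sits in the column headed "Included in objective evaluation of response to therapy and disease reactivation". SAP Appendix A has the same structure, with two uveitis rows on the mAIDAI side and a single uveitis row on the objective side.

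SAP 7.4.4.4 then sets out the component analysis: "The number and percent of patients who improve within each component (objective and subjective) of the mAIDAI will be summarized during the RW phase". The denominator is given as: "For each component, only the number of patients who reported the assessment as present (1 or 2) will be considered for analysis". Improvement is defined through the patients who "report the assessment as absent (0, ie, improved relative to baseline) at each post-baseline visit", and the arms are compared on that proportion by Fisher's exact test. The same section asks for present/absent shift tables by component in the RW phase, and for improvement counts and shift tables by visit in the SAOL phase. No sentence in that section links the two uveitis rows.

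**The concern.** Calling an absent component improved is sound for thirteen of the fourteen rows only if each row stands for a sign that can be present or gone on its own. The two uveitis rows do not. They are adjacent grade bands of one sign, so a patient can leave the lower band by getting worse. A rule that looks at the 1+/2+ row alone cannot tell resolution from progression.

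At stake is the direction of the reported change in eye disease. Protocol 14.3 names the severity and evolution of uveitis as something to be assessed. SAP 7.5.5.6 only lists the ophthalmologic results by patient, so the mAIDAI component tables are where uveitis change is tabulated by visit. Those tables could show a worsening as a benefit.

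**Working it through.** No power or alpha formula applies. The check is to confirm which items the component analysis uses, and then to apply the rule to each change of grade.

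**1. Item count.** The Appendix 1 columns are fever, abdominal pain, nausea/vomiting, diarrhea, transaminitis, organomegaly, rash, uveitis 3+/4+, uveitis 1+/2+, arthralgia, arthritis, radiologic CNS involvement, CNS symptoms and cytopenia. That is 14, of which 4 are marked subjective, which reproduces the figure in Protocol 10.5. The count reaches 14 only if uveitis is two items.

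**2. Which form SAP 7.4.4.4 uses.** Its denominator allows a present score of 1 or 2. In Appendix 1 only the 3+/4+ row can score 2. On the objective side of SAP Appendix A every item scores at most 1. The component analysis as written therefore works on the ungrouped rows.

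**3. Rule applied, one grade recorded per visit** (P = present, A = absent; improvement is assessed only if the row is present at baseline):

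| Change | 3+/4+ row | 1+/2+ row | mAIDAI total | Merged objective category |
|---|---|---|---|---|
| 1+/2+ to none | A to A, not in denominator | P to A, improved | -1 | -1 |
| 3+/4+ to none | P to A, improved | A to A, not in denominator | -2 | -1 |
| 1+/2+ to 3+/4+ | A to P, not in denominator | P to A, **improved** | +1 | 0 |
| 3+/4+ to 1+/2+ | P to A, improved | A to P, **newly present** in the shift table | -1 | 0 |

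The third line is the error. The patient was not in the 3+/4+ denominator, so the improvement tables carry the false improvement and nothing to offset it. The fourth line is a lesser fault and concerns the shift table only.

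**4. Rule applied, both rows ticked for 3+/4+.** Worsening from 1+/2+ leaves the 1+/2+ row present, so it is not improved. Recovery to 1+/2+ also leaves that row present, so it is not new. Neither artefact occurs. A 3+/4+ eye would then add 2 + 1 = 3 to the total.

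**5. Size in the tables.** With 5 patients per RW arm (SAP 7.6), one patient is 1/5 = 20 points of an arm's percentage if all five have the row present at RW baseline, and 1/1 = 100 points if only one does.

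**6. Could the Fisher comparison reach p < 0.05?** Take complete separation between arms, the most extreme case. With six patients having the row present at RW baseline:
- 3 v 3: p = 2/20 = 0.10
- 4 v 2: p = 1/15 = 0.067
- 5 v 1: p = 1/6 = 0.167

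With seven patients:
- 4 v 3: p = 1/35 = 0.029
- 5 v 2: p = 1/21 = 0.048

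At least 7 of the 10 randomised patients would need the same uveitis row present at RW baseline.

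**The case against.** The best reply is that a present score of 1 or 2 would also fit a single uveitis component coded 0/1/2. On that reading a rise in grade is present to present, and the SAP is merely silent. Alternatively, the programmers might use the single uveitis row in SAP Appendix A, which is labelled for efficacy evaluation. Neither reading is written down. No 0/1/2 uveitis component appears in either document, and the merged row cannot score 2. The rule as written applies to the rows that Appendix 1 lists as components.

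Several other parts of the reply stand:
- The artefact depends on one grade being recorded per visit. The documents do not say so. Disjoint grade bands weighted 1 and 2 make it the natural reading, and completion guidelines not available here may settle it.
- SAP 7.4.5.5 places the component tests outside the fixed sequence, as descriptive.
- The 3+/4+ shift table, the mAIDAI total and the patient listings show the true direction. With at most 15 enrolled patients they can be read case by case.
- Protocol Table 1 schedules a formal ophthalmic examination only at V1, so changes of grade may seldom be recorded.

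A reader might go further and infer that the confirmatory sequence is at risk, because ticking both rows would make severe uveitis worth 3 points in the mAIDAI total (step 3). The documents do not support that. Nothing in them suggests that both rows would be ticked, and with one row ticked the total moves correctly. The two problems also exclude each other: the direction artefact needs one row ticked, the 3-point score needs both.

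**Conclusion.** The point holds as a minor defect in descriptive output. Under SAP 7.4.4.4 as written, and assuming one grade per visit, worsening from 1+/2+ to 3+/4+ is counted as improved in the 1+/2+ row of the SAOL and RW improvement tables and in the RW Fisher comparison. Recovery from 3+/4+ to 1+/2+ appears as newly present in the 1+/2+ shift table.

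The primary endpoint, treatment failure, response to therapy and RW eligibility are unaffected, because they use the merged category. The grouping note in Appendix 1 is what protects them; it is not the fault. A reader might also conclude that every patient whose grade changes is certain to be misclassified. That is too strong, since it rests on how the two boxes are completed. The documents give no uveitis frequency, so the number affected is unknown. It is probably small, since RW entrants must already be partial or complete responders.

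**What to change.** In SAP 7.4.4.4, state that the component improvement and shift tables use one combined uveitis item. Either of two forms would do:
- present/absent, as in the objective column of SAP Appendix A, so that a change of grade is neither improved nor new; or
- graded none, 1+/2+, 3+/4+, with improved meaning a lower level than baseline and worsened a higher one.

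The first keeps the present/absent approach that Protocol 8.3.1 argues for. The second also shows partial recovery. Under both, a rise in grade cannot count as improvement. Add that the two grade rows exclude each other, so that uveitis adds at most 2 to the mAIDAI total.

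The cost is two sentences and one derived variable. No new data are needed, and no endpoint definition or confirmatory test changes.

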APPENDIX 2: LOCAL TOLERABILITY INDEX

Pain

Description

NONE
MILD
MODERATE
SEVERE

The subjects will be asked to assess the degree of pain they are experiencing from each injection.

Redness**Description**

NONE	No visible redness
MILD	0 to 2 cm redness
MODERATE	2.1 to 5 cm redness
SEVERE	Greater than or equal to 5.1 cm redness

The subjects will be asked to assess the amount of redness they are experiencing from each injection as per the above guidance.

Swelling**Description**

NONE	No swelling detected
MILD	Palpable "firmness" only
MODERATE	< 4 cm swelling
SEVERE	≥ 4 cm swelling

The subjects will be asked to assess the amount of swelling they are experiencing from each injection as per the above guidance.

Bruising**Description**

NONE	No visible bruising
MILD	0 to 2cm bruising
MODERATE	2.1 to 5cm bruising
SEVERE	Greater than or equal to 5.1 cm bruising

The subjects will be asked to assess any bruising that they experience with each injection as per above the guidance.

Tenderness**Description**

NONE
MILD
MODERATE
SEVERE

The subjects will be asked to note the degree of tenderness they are experiencing from each injection

Itching**Description**

[figure not shown]
NONE
MILD
MODERATE
SEVERE

The subjects will be asked to note the degree of itching they are experiencing from each injection.

APPENDIX 3: PHYSICIAN GLOBAL ASSESSMENT OF DISEASE-RELATED (AUTOINFLAMMATORY) SYMPTOMS - QUESTIONS FOR INVESTIGATORS

INSTRUCTIONS: Complete the following questions for each patient at each clinic visit to assess the patient's level of disease-related symptoms.

1. Using the 0 to 10 scale below where 0 is **Not at All Severe** and 10 is **Very Severe**, please mark an "X" in the box (☒) which best describes your medical assessment of the severity of the subject's disease-related (autoinflammatory) symptoms at this visit.

At this visit, how severe are the patient's disease-related (autoinflammatory) symptoms?										

Not at All Severe  Very Severe 
 
0 1 2 3 4 5 6 7 8 9 10
 										

2. **Clinical stability:** This question regarding the clinical stability of disease-related (autoinflammatory) symptoms over the past two weeks will be used to determine if the subject's symptoms have been stable, improved or gotten worse.
Please mark an "X" in the box (☒) which best describes your medical assessment of the stability of the subject's disease-related (autoinflammatory) symptoms over the past two weeks.

	Stable
	Improved
	Worse

KEY TO SYMPTOM SEVERITY FOR QUESTION #1

Score	Rating	Impact on Subject	Severity Key
0	None	No Impact	No Symptoms
1	Mild	Does Not Interfere With Activities	Mild Symptoms Not Associated With Discomfort
2			Mild Symptoms Associated With Discomfort
3	Moderate	Interferes With Activities	Moderate Symptoms With A Limited Impact On Usual Activities
4			Moderate Symptoms With A Moderate Impact On Usual Activities
5			Moderate Symptoms With A Marked Impact On Usual Activities
6	Severe	Interferes With Activities, Requires Lifestyle Change	Severe Symptoms Requiring Some Changes In Lifestyle
7			Severe Symptoms Requiring Major Changes In Life Style
8	Very Severe	Prevents From Engaging With Normal Activities	Very Severe Symptoms Preventing From Engaging In Most Normal Activities
9			Very Severe Symptoms Completely Preventing From Engaging In Normal Activities
10	Extreme	No Normal Activities Possible	Extreme Symptoms

APPENDIX 4: DECLARATION OF HELSINKI

WMA Declaration of Helsinki - Ethical Principles for Medical Research Involving Human Subjects

Adopted by the 18th WMA General Assembly, Helsinki, Finland, June 1964 and amended by the: 29th WMA General Assembly, Tokyo, Japan, October 1975 35th WMA General Assembly, Venice, Italy, October 1983 41st WMA General Assembly, Hong Kong, September 1989 48th WMA General Assembly, Somerset West, Republic of South Africa, October 1996

52nd WMA General Assembly, Edinburgh, Scotland, October 2000 53rd WMA General Assembly, Washington DC, USA, October 2002 (Note of Clarification added) 55th WMA General Assembly, Tokyo, Japan, October 2004 (Note of Clarification added) 59th WMA General Assembly, Seoul, Republic of Korea, October 2008 64th WMA General Assembly, Fortaleza, Brazil, October 2013

Preamble

1. The World Medical Association (WMA) has developed the Declaration of Helsinki as a statement of ethical principles for medical research involving human subjects, including research on identifiable human material and data.

The Declaration is intended to be read as a whole and each of its constituent paragraphs should be applied with consideration of all other relevant paragraphs.

2. Consistent with the mandate of the WMA, the Declaration is addressed primarily to physicians. The WMA encourages others who are involved in medical research involving human subjects to adopt these principles.

General Principles

3. The Declaration of Geneva of the WMA binds the physician with the words,

"The health of my patient will be my first consideration," and the International Code of Medical Ethics declares that, "A physician shall act in the patient's best interest when providing medical care."

4. It is the duty of the physician to promote and safeguard the health, well-being and rights of patients, including those who are involved in medical research. The physician's knowledge and conscience are dedicated to the fulfilment of this duty.

5. Medical progress is based on research that ultimately must include studies involving human subjects.

6. The primary purpose of medical research involving human subjects is to understand the causes, development and effects of diseases and improve preventive, diagnostic and therapeutic interventions (methods, procedures and treatments). Even the best proven interventions must be evaluated continually through research for their safety, effectiveness, efficiency, accessibility and quality.

7. Medical research is subject to ethical standards that promote and ensure respect for all human subjects and protect their health and rights.

8. While the primary purpose of medical research is to generate new knowledge, this goal can never take precedence over the rights and interests of individual research subjects.

9. It is the duty of physicians who are involved in medical research to protect the life, health, dignity,

integrity, right to self-determination, privacy, and confidentiality of personal information of research subjects. The responsibility for the protection of research subjects must always rest with the physician or other health care professionals and never with the research subjects, even though they have given consent.

10. Physicians must consider the ethical, legal and regulatory norms and standards for research involving human subjects in their own countries as well as applicable international norms and standards. No national or international ethical, legal or regulatory requirement should reduce or eliminate any of the protections for research subjects set forth in this Declaration.

11. Medical research should be conducted in a manner that minimises possible harm to the environment.

12. Medical research involving human subjects must be conducted only by individuals with the appropriate ethics and scientific education, training and individuals with the appropriate ethics and scientific education, training and qualifications. Research on patients or healthy volunteers requires the supervision of a competent and appropriately qualified physician or other health care professional.

13. Groups that are underrepresented in medical research should be provided appropriate access to participation in research.

14. Physicians who combine medical research with medical care should involve their patients in research only to the extent that this is justified by its potential preventive, diagnostic or therapeutic value and if the physician has good reason to believe that participation in the research study will not adversely affect the health of the patients who serve as research subjects.

15. Appropriate compensation and treatment for subjects who are harmed as a result of participating in research must be ensured.

Risks, Burdens and Benefits

16. In medical practice and in medical research, most interventions involve risks and burdens.

Medical research involving human subjects may only be conducted if the importance of the objective outweighs the risks and burdens to the research subjects.

17. All medical research involving human subjects must be preceded by careful assessment of predictable risks and burdens to the individuals and groups involved in the research in comparison with foreseeable benefits to them and to other individuals or groups affected by the condition under investigation.

Measures to minimise the risks must be implemented. The risks must be continuously monitored, assessed and documented by the researcher.

18. Physicians may not be involved in a research study involving human subjects unless they are confident that the risks have been adequately assessed and can be satisfactorily managed.

When the risks are found to outweigh the potential benefits or when there is conclusive proof of definitive outcomes, physicians must assess whether to continue, modify or immediately stop the study.

Vulnerable Groups and Individuals

19. Some groups and individuals are particularly vulnerable and may have an increased likelihood of being wronged or of incurring additional harm.

All vulnerable groups and individuals should receive specifically considered protection.

20. Medical research with a vulnerable group is only justified if the research is responsive to the health needs or priorities of this group and the research cannot be carried out in a non-vulnerable group. In addition, this group should stand to benefit from the knowledge, practices or interventions that result from the research.

Scientific Requirements and Research Protocols

21. Medical research involving human subjects must conform to generally accepted scientific principles, be based on a thorough knowledge of the scientific literature, other relevant sources of information, and adequate laboratory and, as appropriate, animal experimentation. The welfare of animals used for research must be respected.

22. The design and performance of each research study involving human subjects must be clearly described and justified in a research protocol.

The protocol should contain a statement of the ethical considerations involved and should indicate how the principles in this Declaration have been addressed. The protocol should include information regarding funding, sponsors, institutional affiliations, potential conflicts of interest, incentives for subjects and information regarding provisions for treating and/or compensating subjects who are harmed as a consequence of participation in the research study.

In clinical trials, the protocol must also describe appropriate arrangements for post-trial provisions.

Research Ethics Committees

23. The research protocol must be submitted for consideration, comment, guidance and approval to the concerned research ethics committee before the study begins. This committee must be transparent in its functioning, must be independent of the researcher, the sponsor and any other undue influence and must be duly qualified. It must take into consideration the laws and regulations of the country or countries in which the research is to be performed as well as applicable international norms and standards but these must not be allowed to reduce or eliminate any of the protections standards but these must not be allowed to reduce or eliminate any of the protections for research subjects set forth in this Declaration.

The committee must have the right to monitor ongoing studies. The researcher must provide monitoring information to the committee, especially information about any serious adverse events. No amendment to the protocol may be made without consideration and approval by the committee. After the end of the study, the researchers must submit a final report to the committee containing a summary of the study's findings and conclusions.

Privacy and Confidentiality

24. Every precaution must be taken to protect the privacy of research subjects and the confidentiality of their personal information.

Informed Consent

25. Participation by individuals capable of giving informed consent as subjects in medical research must be voluntary. Although it may be appropriate to consult family members or community leaders,

no individual capable of giving informed consent may be enrolled in a research study unless he or she freely agrees.

26. In medical research involving human subjects capable of giving informed consent, each potential subject must be adequately informed of the aims, methods, sources of funding, any possible conflicts of interest, institutional affiliations of the researcher, the anticipated benefits and potential risks of the study and the discomfort it may entail, post-study provisions and any other relevant aspects of the study. The potential subject must be informed of the right to refuse to participate in the study or to withdraw consent to participate at any time without reprisal. Special attention should be given to the specific information needs of individual potential subjects as well as to the methods used to deliver the information.

After ensuring that the potential subject has understood the information, the physician or another appropriately qualified individual must then seek the potential subject's freely-given informed consent, preferably in writing. If the consent cannot be expressed in writing, the non-written consent must be formally documented and witnessed.

All medical research subjects should be given the option of being informed about the general outcome and results of the study.

27. When seeking informed consent for participation in a research study the physician must be particularly cautious if the potential subject is in a dependent relationship with the physician or may consent under duress. In such situations the informed consent must be sought by an appropriately qualified individual who is completely independent of this relationship.

28. For a potential research subject who is incapable of giving informed consent, the physician must seek informed consent from the legally authorised representative. These individuals must not be included in a research study that has no likelihood of benefit for them unless it is intended to promote the health of the group represented by the potential subject, the research cannot instead be performed with persons capable of providing informed consent, and the research entails only minimal risk and minimal burden.

29. When a potential research subject who is deemed incapable of giving informed consent is able to give assent to decisions about participation in research, the physician must seek that assent in addition to the consent of the legally authorised representative. The potential subject's dissent should be respected.

30. Research involving subjects who are physically or mentally incapable of giving consent, for example, unconscious patients, may be done only if the physical or mental condition that prevents giving informed consent is a necessary characteristic of the research group. In such circumstances the physician must seek informed consent from the legally authorised representative. If no such representative is available and if the research cannot be delayed, the study may proceed without informed consent provided that the specific reasons for involving subjects with a condition that renders them unable to give informed consent have been stated in the research protocol and the study has been approved by a research ethics committee. Consent to remain in the research must be obtained as soon as possible from the subject or a legally authorised representative.

31. The physician must fully inform the patient which aspects of their care are related to the research. The refusal of a patient to participate in a study or the patient's decision to withdraw from the study must never adversely affect the patient- physician relationship.

32. For medical research using identifiable human material or data, such as research on material or data contained in biobanks or similar repositories, physicians must seek informed consent for its collection, storage and/or reuse. There may be exceptional situations where consent would be impossible or impracticable to obtain for such research. In such situations the research may be done only after for such research. In such situations the research may be done only after consideration

and approval of a research ethics committee.

Use of Placebo

33. The benefits, risks, burdens and effectiveness of a new intervention must be tested against those of the best proven intervention(s), except in the following circumstances:

Where no proven intervention exists, the use of placebo, or no intervention, is acceptable; or

Where for compelling and scientifically sound methodological reasons the use of any intervention less effective than the best proven one, the use of placebo, or no intervention is necessary to determine the efficacy or safety of an intervention and the patients who receive any intervention less effective than the best proven one, placebo, or no intervention will not be subject to additional risks of serious or irreversible harm as a result of not receiving the best proven intervention.

Extreme care must be taken to avoid abuse of this option.

Post-Trial Provisions

34. In advance of a clinical trial, sponsors, researchers and host country governments should make provisions for post-trial access for all participants who still need an intervention identified as beneficial in the trial. This information must also be disclosed to participants during the informed consent process.

Research Registration and Publication and Dissemination of Results

35. Every research study involving human subjects must be registered in a publicly accessible database before recruitment of the first subject.

36. Researchers, authors, sponsors, editors and publishers all have ethical obligations with regard to the publication and dissemination of the results of research. Researchers have a duty to make publicly available the results of their research on human subjects and are accountable for the completeness and accuracy of their reports. All parties should adhere to accepted guidelines for ethical reporting. Negative and inconclusive as well as positive results must be published or otherwise made publicly available. Sources of funding, institutional affiliations and conflicts of interest publicly available. Sources of funding, institutional affiliations and conflicts of interest must be declared in the publication. Reports of research not in accordance with the principles of this Declaration should not be accepted for publication.

Unproven Interventions in Clinical Practice

37. In the treatment of an individual patient, where proven interventions do not exist or other known interventions have been ineffective, the physician, after seeking expert advice, with informed consent from the patient or a legally authorised representative, may use an unproven intervention if in the physician's judgement it offers hope of saving life, re-establishing health or alleviating suffering. This intervention should subsequently be made the object of research, designed to evaluate its safety and efficacy. In all cases, new information must be recorded and, where appropriate, made publicly available.

© World Medical Association, Inc. - All Rights reserved. © Asociación médica mundial - Todos los derechos reservados. © L'Association Médicale Mondiale - Tous droits réservés.

Disclaimer: © 2013 World Medical Association, Inc. All Rights Reserved. All intellectual property rights in the Declaration of Helsinki are vested in the World Medical Association. Previous permissions granted to publish or reproduce otherwise WMA policy don't apply to this version of the Declaration of Helsinki until January 1st, 2014. For further questions, please contact the WMA secretariat at [contact].

